2.6.2 Potential Benefits

This is the OLE to the first-in-human study of ARCT-021 so it is not known if there will be any direct benefits to subjects participating in the study. If ARCT-021 is effective as a vaccine, then subjects may get effective protection against COVID-19. There is an indirect societal benefit of gaining medical knowledge to further develop ARCT-021.

2.7 Ethical Considerations

There are no relevant ethical considerations.

3 EXPERIMENTAL PLAN

3.1 Compliance

The study will be conducted in compliance with this clinical study protocol, International Conference on Harmonization (ICH) Good Clinical Practices (GCP), as outlined by ICH E6(R2) and subsequent amendments, as well as the demands of national drug and data protection laws and all applicable local and national regulatory requirements.

3.2 Study Design

This is an open label study enrolling healthy adult subjects that participated in Study ARCT-021-01 (the Parent Study). Subjects will enter this study approximately 3 months after their final study visit in the Parent Study.

Subjects who received placebo and subjects who received a single injection of ARCT-021 in the Parent Study and are seronegative for SARS-CoV-2 PRNT50 neutralising antibodies at screening will receive a single injection of ARCT-021 in this study at a 7.5 µg dose level.

Subjects who received two injections of ARCT-021 in the Parent Study and subjects who received a single injection of ARCT-021 but are seropositive for SARS-CoV-2 PRNT50 neutralising antibodies at screening will not receive any further injections of ARCT-021 in this study.

ARCT-021 will be administered by IM injection into the lateral aspect of the deltoid muscle of the non-dominant arm.

Subjects should remain at the center for at least 30 minutes for observation following vaccine administration.

Epinephrine for subcutaneous injection, diphenhydramine for intravenous injection, and any other medications and resuscitation equipment for the emergency management of anaphylactic reactions must be available in close proximity in the room where the vaccination is administered.

If the subject experiences a severe reaction following vaccine administration, the CRO Medical Monitor should be contacted as soon as feasible to discuss if additional assessments may be clinically warranted prior to the discharge of the subject from the study center.

3.3 Measures to Minimize/Avoid Bias

Critical study end points will be pre-specified in the Statistical Analysis Plan. As this is an OLE to the Parent Study other measures to minimize bias are not relevant.

3.4 Quality Control and Quality Assurance

Quality control (QC) and quality assurance measures include:

- On-site and remote monitoring of sites by Sponsor (or designee) with 100% source data verification to ensure compliance with protocol and accuracy of data collection/transcription
- Remote Sponsor (or designee) review of study protocol compliance and study data with issuance of data queries to correct errors as appropriate
- Audit of study centre as required
- Retraining of site staff as required

3.5 Number of Study Centers

This study will be conducted at a single center in Singapore.

3.6 Number of Subjects

If all subjects who were treated in Parent Study consent to enroll in this study and meet the eligibility criteria then approximately 99 subjects, up to a maximum of 166 subjects will be enrolled.

3.7 Overall Study Duration and Follow-up

The duration of participation is designed such that all subjects will be followed up until at least 12 months after their last injection of ARCT-021, irrespective of whether the last injection was in the Parent Study or in this study.

Subjects who are not receiving ARCT-021 in this study

The study comprises an up to a 4-week Screening Period followed by a 9-month observation period. The length of each subject's participation is approximately 10 months from screening to last study visit.

Subjects receiving a single injection of ARCT-021

The study comprises an up to 4-week Screening Period, a 1-day Study Drug Administration Period and a 12-month Post Treatment observation period. The length of each subject's participation is approximately 13 months from screening to last study visit.

3.8 Study Visit Schedule

Detailed Information regarding the study is contained in [Appendix 1](#).

Subjects will be instructed to contact the study site staff immediately if they receive a diagnosis of SARS-COV-2 infection or COVID-19 or if they experience an adverse event that requires them to seek medical attention or if they become hospitalized. In addition, subjects receiving ARCT-021 in this study will be instructed to contact the study site staff immediately if they experience a grade 3 or above solicited AE. Any subject with exposure to a confirmed COVID-19

case or confirmed SARS-CoV-2 infection, or that reports symptoms suggestive of possible COVID-19 infection (Section 6.2.4) should undergo testing by PCR to determine if the subject may have COVID-19 or SARS-CoV-2 infection. (Sections 6.2.4 and 9.5.5). The Investigator will make reasonable efforts to perform a SARS-CoV-2 PCR test preferably within 72 hours to confirm diagnosis.

Any subject that develops PCR confirmed SARS-CoV-2 infection may have subsequent study visits performed in hospital. Subjects should be reminded to contact the site within 24 hours if experiencing COVID-19-like symptoms (Section 6.2.4) or if exposed to a confirmed COVID-19 case or person with confirmed SARS-CoV-2 infection.

In addition to the visit schedule described below, subjects may be required to attend additional visits for monitoring of adverse events or abnormal investigation results.

3.8.1 Screening

Informed consent (Section 4.1) and subject eligibility for the study will be determined within 28 days prior to study Day 1. A screen failure is defined as any individual who participated in the ARCT-021-01 study and does not consent to participate in the ARCT-021-02, any individual who does not enter screening procedures, any individual who does not meet entry criteria for the ARCT-021-02 study or any individual who withdraws consent for participation in the ARCT-021-02 prior to Day 1 study procedures.

3.8.2 Study Drug Administration

Subjects receiving a single injection of ARCT-021

ARCT-021 will be administered on Day 1 following Baseline evaluations. Subjects will be observed for at least 30 minutes after dosing. After this, subjects may remain at the study center or be discharged.

3.8.3 Post Treatment

Subjects who are not receiving ARCT-021 in this study

Subjects will have visits on Day 1, Day 29, Day 85, Day 197 and Day 281. The Final visit will be on Day 281.

Subjects receiving a single injection of ARCT-021

Subjects will return for outpatient visits on Days 8, 15, 29, 57, 169, 253 and 365. The final visit will be on Day 365.

3.9 End-of-Study

The End-of-Study is last subject, last visit.

Subjects who terminate from the study before completion will be told to inform the Study Site staff if they develop symptoms compatible with COVID-19 (Section 6.2.4) or a diagnosis of SARS-CoV-2 infection or COVID-19 until 1 year post last dose of ARCT-021 so that they can be adequately followed up. Reporting instructions for cases of PCR-confirmed SARS-CoV-2 infection and COVID-19 are contained in Section 9.5.5.

3.10 Study Stopping Criteria

As this is an extension study to determine long-term safety there are no stopping criteria for the study.

Stopping rules for dosing of individual subjects are found in Section [8.6](#)

4 SUBJECT ENROLLMENT

4.1 Informed Consent

Before subjects may be enrolled into the study, the Sponsor or designee requires a copy of the Study Center's written independent ethics committee (IEC)/institutional review board (IRB) approval of the protocol, informed consent form, and all other subject information and/or recruitment material, as applicable.

Subjects must sign the consent form before any screening tests or study assessments are performed. At the time of consent, the subject will be considered enrolled into the study and will be assigned a screening number before any study procedures, including Screening procedures, are performed. Once eligibility is confirmed subjects will be assigned a subject number. This number will be used to identify the subject throughout the trial and must be used on all study documentation related to that subject. Subject identification number must remain constant throughout the entire trial. **Subjects in this study will keep the same screening number and subject number as in the Parent Study.**

5 SUBJECT ELIGIBILITY

To be eligible to participate in this study candidates must meet the following eligibility criteria within 28 days prior to Study Day 1. Subjects who fail screening due to out of range lab values may have these labs retested up to two times, subject to approval by the Sponsor Medical Monitor (or designee), to determine eligibility.

5.1 Inclusion Criteria

1. Must have given written informed consent (signed and dated) and any authorizations required by local law and be able to comply with all study requirements
2. Must have completed Study ARCT-021-01 without early termination
3. Willing and able to comply with all protocol-defined procedures and complete all study visits

Only for subjects that will receive ARCT-021 in this study:

4. Are healthy in the opinion of the Investigator
5. Temperature is less than 99.3 degrees Fahrenheit (37.4 degrees Celsius) at screening AND at the pre-dose evaluation on Day 1 (if temperature is higher than this range at Day 1 then please refer to Section [8.7.1](#))
6. Willing to refrain from donating blood or plasma from signing of the informed consent until 28 days after the last dose of ARCT-021.

7. Willing to refrain from strenuous exercise/activity (for example heavy lifting, weight training, intense aerobics classes etc.) and alcohol for at least 72 hours prior to study visits until 28 days after the last dose of ARCT-021.
8. Males must be surgically sterile or, if engaged in sexual relations with a female of child-bearing potential, the subject must be using an acceptable contraceptive method (refer to Section 6.3.1) from the time of signing the informed consent form until at least 56 days after the last dose of Study Drug.

Male subjects with partners that are pregnant must use condoms until at least 56 days after the last dose of Study Drug to ensure that the fetus is not exposed to the Study Drug.

Male subjects must refrain from sperm donation from the time of signing the informed consent form until at least 56 days after the last dose of Study Drug.

Note: Males who are incapable of fathering a child (documented bilateral vasectomy with confirmation of aspermia or bilateral orchiectomy) will not be required to use birth control during the study.

Females: must be non-pregnant and non-lactating and either:

- i. surgically sterile (e.g., tubal occlusion, hysterectomy, bilateral salpingectomy, bilateral oophorectomy);
- ii. post-menopausal (defined as 12 months of spontaneous amenorrhea in females > 55 years of age or, in females ≤ 55 years, 12 months of spontaneous amenorrhea without an alternative medical cause and FSH levels in the postmenopausal range for the laboratory involved);
- iii. if engaged in sexual relations and of child-bearing potential, agree to use 2 highly effective contraceptive methods (refer to Section 6.3.1) from the time of signing the informed consent form until at least 56 days after the last dose of Study Drug

For female subjects and female partners of male subjects, highly effective female contraception methods comprise surgical sterilization (e.g., bilateral tubal occlusion), hormonal contraception associated with inhibition of ovulation (combined estrogen and progestogen containing, or progestogen-only), intrauterine contraception device or intrauterine hormone-releasing system (IUS).

Women of childbearing potential (WOCBP) must refrain from egg donation from the time of signing the informed consent form until at least 56 days after the last dose of Study Drug.

5.2 Exclusion Criteria

1. Significant (as determined by Principal Investigator) noncompliance with the study visits or procedures in Study ARCT-021-01
2. Any subject that received placebo in the Parent Study and who is not willing to receive ARCT-021 in this study.

Only for subjects that will receive ARCT-021 in this study:

- 3 Receipt of any other SARS CoV-2 or other experimental coronavirus vaccine since completion of the Parent Study or planned during this study.

4. Diagnosis of new clinically significant abnormalities in medical history or physical examination since enrolment in the Parent Study, including but not limited to:
 - Respiratory disease (e.g., chronic obstructive pulmonary disease [COPD], asthma) requiring daily medications or oxygen currently or any treatment of respiratory disease exacerbations (e.g., COPD or asthma exacerbation) warranting hospitalization or an emergency room visit or supplemental oxygen.
 - Significant cardiovascular disease (e.g., congestive heart failure, cardiomyopathy, ischemic heart disease), myocarditis or pericarditis.
 - Neurological or neurodevelopmental conditions (e.g., migraines, epilepsy, stroke, seizures, encephalopathy, focal neurologic deficits, Guillain-Barré syndrome, encephalomyelitis or transverse myelitis).
 - New diagnosis of a significant hematologic abnormality (e.g., sickle cell disease, beta thalassemia)
 - New Diagnosis of autoimmune disease as listed by the American Autoimmune Related Disease Association ([Appendix 3](#))
 - Major surgery
5. Screening laboratory results as follows, or any other clinically significant abnormalities in screening laboratory values that would render a subject unsuitable for inclusion
 - ALT, AST, GGT, total bilirubin or alkaline phosphatase, > ULN unless approved by Sponsor Medical Monitor (or designee).
 - Hb <10 g/dL for females and <12 g/dL for males
 - Platelet count < 100x10⁹/L
 - eGFR < 50 ml/min/1.73m² calculated by Modification to Diet in Renal Disease [MDRD] study equation, unless approved by the Sponsor Medical Monitor (or designee)
6. Diabetes that is not, in the opinion of the investigator, adequately controlled with diet +/- antidiabetic medication
7. Use of any prescription or over-the-counter medications within 7 days prior to vaccination, unless approved by the Sponsor Medical Monitor (or designee).
8. Received immunoglobulins and/or any blood or blood products since completion of the Parent Study.
9. Has any blood dyscrasias or significant disorder of coagulation.
10. Uncontrolled hypertension (BP > 160/100 mm Hg)
11. Treatment with another investigational drug, biological agent, or device since completion of the Parent Study
12. Received or plans to receive:
 - A licensed, live vaccine within 4 weeks before or after study vaccination, or

- A licensed, inactivated vaccine within 2 weeks before or after study vaccination.

13. Has traveled outside of Singapore within 30 days before the vaccination or planned travel outside of Singapore within 60 days after vaccination.

14. Have any other conditions, which, in the opinion of the Investigator or Sponsor would make the subject unsuitable for inclusion, or could interfere with the subject participating in or completing the Study

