Subjects that are not receiving ARCT-021 in this study

All participants who received 2 injections of ARCT-021 as part of participation in Cohorts E, F, G, and H in Study ARCT-021-01 and any participant who received 1 injection of ARCT-021 in Cohorts A, B, C, D1 and D2 in Study ARCT-021-01 AND who is seropositive by SARS-CoV-2 PRNT50 neutralising antibody test at screening in this study (ARCT-021-02).

The study comprises an up to a 4-week Screening Period followed by a 9-month observation period. The length of each subject's participation is approximately 10 months from screening to last study visit.

After screening subjects will return for outpatient visits on Days 1, 29, 85, 197 and then 281. The final visit will be on Day 281.

Subjects that do not receive ARCT-021 in this study will not have any further laboratory safety evaluations performed in this study and only Serious Adverse Events (SAE) and Medically Attended AE (MAAE) will be recorded. Subjects will be instructed to contact the study site staff immediately if they experience an adverse event that requires them to seek medical attention or if they become hospitalised.

Subjects receiving ARCT-021

All participants who received placebo as part of participation in Study ARCT-021-01 and any participant who received 1 injection of ARCT-021 in Cohorts A, B, C, D1 and D2 in Study ARCT-021-01 AND who is seronegative by SARS-CoV-2 PRNT50 neutralising antibody test at screening in this study (ARCT-021-02).

Blood and urine samples will be collected for safety evaluations up to 28 days after the last injection of ARCT-021 ([Appendix 1](#)).

Local and systemic solicited and unsolicited AEs will be recorded daily by the subject in a symptom diary for at least 7 days post vaccination and up to 14 days post vaccination if any events are persisting at 7 days (Section [6.2.1](#) and [Appendix 1](#)).

[figure not shown]

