Enhancement of respiratory disease if subsequently infected with SARS-CoV-2	Vaccine- associated enhanced respiratory disease has been observed following other vaccinations (de Alwis 2020 ; Polack 2007). This is thought to be mediated by an abnormal Th1/Th2 response that is biased towards Th2 (de Alwis 2020 ; Acosta 2016 ; Polack 2007) and/or failure to generate a strong neutralising antibody response (Polack 2007). Since older individuals are more at risk of severe respiratory symptoms this risk may be greater for this age group.	
 • Vaccination of mice with ARCT-021 produced robust neutralising antibody and CD8+ T-cell response and a balanced, Th1-biased Th1/Th2 response across all doses (Section 2.5.3) • Eligibility criteria for the Parent Study ARCT-021-01 exclude subjects with major comorbidities that increase risk for severe COVID-19 (Section 5.2). • Th1/Th2 responses will have been assessed in Study ARCT-021-01 prior to vaccination of subjects in this study • Explanation of the theoretical risks of enhanced COVID-19 disease as a consequence of ARCT-021 administration will be included as part of informed consent process. (Section 11.1) • Subjects that enroll in this study will be followed for 1-year after their last injection of ARCT-021 (Section 3.9) • For the duration of participation in the study and at the time of termination of study participation, subjects will be told to inform the Investigator if they develop symptoms compatible with COVID-19 or a diagnosis of SARS-CoV-2 infection or COVID-19 so that they can be adequately followed up (Section 3.9).

SRC= Safety Review Committee; Th = T-helper cell;

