8.1.9.1 Unsolicited Adverse Event Summaries

All unsolicited AEs (serious and non-serious) occurring after exiting Parent study and after administration of first dose of study vaccine (in this study or parent study as applicable) and before the End of Study or Off-study vaccination, regardless of relationship to study vaccine, will be included and classified by system organ class (SOC) and preferred term (PT) using the Medical Dictionary for Regulatory Activities (MedDRA).

- For Cohort 1a, AE occurring from the time of exiting the Parent Study up to receipt of Study Vaccine on Day 1 will be regarded as medical history. All unsolicited events, including SAEs, MAAEs, and NOCD are collected up to 28 days after receipt of study vaccine and only SAEs, MAAEs, and NOCD are collected beyond 28 days after receipt of study vaccine.
- For Cohort 1b, SAEs, MAAEs, and NOCD occurring from the time of exiting the Parent Study up to receipt of study vaccine on Day 1 will be regarded as treatment emergent but will be presented separately (as 'Pre-Study TEAEs') to TEAEs occurring after receipt of vaccine. All unsolicited events, including SAEs, MAAEs, and NOCD are collected up to 28 days after receipt of study vaccine in Study ARCT-021-02 but only SAEs, MAAEs, and NOCD are collected beyond 28 days after receipt of study vaccine.
- For Cohort 2 only SAEs, MAAEs, and NOCD are collected in Study ARCT-021-02 as no further study vaccine is administered in this study. All events reported from the time of exiting the Parent Study up to the data cut point for this interim analysis are regarded as treatment emergent and will be presented merged for the purposes of tabulation.

Solicited systemic and local adverse events will not be included in the unsolicited AE summaries, unless the solicited AE has onset >7 days after administration of Study vaccine or the solicited event is serious or medically attended.

Unsolicited AEs that appear within the Toxicity Grading Scale for Healthy Adult and Adolescent Volunteers Enrolled in Preventive Vaccine Clinical Trials, Sept 2007 will have been entered in the EDC with a numerical Grade (1 to 4). Unsolicited TEAEs that are not contained within this scale will have been graded as mild/moderate/severe. For the purposes of tabulation of unsolicited AEs, events will be presented as mild/moderate/severe, whereby the CRF-designated Grade 1 = mild, Grade 2 = moderate and \geq Grade 3 = severe.

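### Seronegative single-dose recipients who fail the dosing-only criteria have no undosed schedule, so their safety follow-up after Screening depends on not having fallen ill

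*Protocol*

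**What the plan says.** **Routing.** The synopsis (Study Visit Schedule and Procedures) opens the undosed schedule to all two-dose recipients, and to a single-dose recipient "AND who is seropositive by SARS-CoV-2 PRNT50 neutralising antibody test at screening in this study". Protocol Section 3.2 agrees: "subjects who received a single injection of ARCT-021 but are seropositive for SARS-CoV-2 PRNT50 neutralising antibodies at screening will not receive any further injections". Seronegative single-dose recipients are listed with those who will be injected. SAP Section 3.2 repeats the split.

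**Criteria.** In Sections 5.1 and 5.2, inclusions 4 to 8 and exclusions 3 to 14 bind only subjects who will be dosed in this study. Exclusion 4 reads "Diagnosis of new clinically significant abnormalities in medical history or physical examination since enrolment in the Parent Study, including but not limited to", followed by respiratory, cardiovascular, neurological, haematological and autoimmune disease and major surgery. Section 3.8.1 counts as a screen failure "any individual who does not meet entry criteria for the ARCT-021-02 study".

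**Aim and analysis sets.** Section 3.7 says that "all subjects will be followed up until at least 12 months after their last injection of ARCT-021", whichever study that injection was given in. Cohort 2 (Protocol Section 10.2, SAP Section 5.2) is defined by vaccination in the Parent Study and no vaccination here. It carries no serostatus condition.

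**What is kept.** For parent-study vaccinees, SAEs, MAAEs, NOCDs and CESIs since the Parent Study are solicited at Screening (Sections 6.2.1, 9.4.1 and 9.4.2; Appendix 1). Section 9.5.5 requires CESI reporting for one year after vaccination, including for people who did not roll over.

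**The concern.** The primary objective is safety, and the protocol describes the study as an extension to determine long-term safety. Exclusion 4 selects on illness that arose after parent-study enrolment, which is what such an extension exists to observe. For one group of vaccinees, a rule about who may receive a further injection also decides whether the injection already given continues to be followed.

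Two outputs are affected. First, whether the same new diagnosis is followed after Screening depends on antibody status, so Cohorts 1b and 2 are not ascertained alike. Second, SAP Section 8.1.9.1 gives Cohort 1b its own display of between-study events: those occurring "up to receipt of study vaccine on Day 1 will be regarded as treatment emergent but will be presented separately". Membership of Cohort 1b requires having been dosed here. If exclusion 4 is applied as written, that display cannot contain any diagnosis meeting it, and a reader who does not know this could take the absence as evidence of safety.

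**Working it through.** The plan states no figure for this point, so the check is of the allocation rules, followed by the timing.

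**1. Where each parent-study ARCT-021 recipient goes**

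| Parent-study doses | Screening PRNT50 | Dosing-only criteria | Schedule |
|---|---|---|---|
| Two | not in their screening schedule | do not apply | undosed, to Day 281 |
| One | seropositive | do not apply | undosed, to Day 281 |
| One | seronegative | met | dosed, to Day 365 |
| One | seronegative | not met | none stated; screen failure under Section 3.8.1 |

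A new autoimmune diagnosis, for example, leaves subjects in the first two rows under observation. It moves a seronegative single-dose recipient from the third row to the fourth.

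**2. Follow-up left unscheduled**

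Inputs: 57 days in the Parent Study for single-dose cohorts and a nominal 90-day gap (SAP Sections 4.2 and 5.3.2); Screening from Day -28 to Day -1 (Appendix 1); 12 months taken as 365 days.

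- Day 1 here: 57 + 90 = 147 days after parent Day 1, which reproduces the SAP's figure.
- Earliest Screening: 147 - 28 = 119. Remaining: 365 - 119 = 246 days; 246/365 = 67%.
- Latest Screening: 147 - 1 = 146. Remaining: 365 - 146 = 219 days; 219/365 = 60%.

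**3. What the undosed schedule would restore**

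The last undosed visit, Day 281, falls at 147 + 280 = 427 days after parent Day 1. The whole of the missing 219 to 246 days would be covered.

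**4. How many subjects**

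The documents give neither the number of single-dose recipients, nor the seronegative fraction, nor the rate of excluding diagnoses. The following is illustration only, with every input assumed: 30 to 50 single-dose recipients, 25 to 75% seronegative, 2 to 10% with an excluding diagnosis.

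- Expected number lost: from 30 x 0.25 x 0.02 = 0.15 to 50 x 0.75 x 0.10 = 3.75.
- Chance of losing at least one: from 1 - (1 - 0.005)^30 = 14% to 1 - (1 - 0.075)^50 = 98%.

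The range is too wide to say more than that the number is probably small and may be zero.

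**The case against.** The best counter-argument is that the documents are silent and do not expressly expel anyone. The dosing-only criteria do not, on their wording, apply to someone who is not dosed, and Cohort 2 would accept such a subject. That stands as a reason to reconcile the text. It does not supply a route: the synopsis and Section 3.2, which a site would follow, admit single-dose recipients to the undosed schedule only if seropositive.

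Four stronger readings are tempting, and the documents do not support them.

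- *Follow-up ends at parent Day 57, or 56/365 = 15% of the year.* This ignores the Screening visit, where interim events are solicited. For those who consent and attend, 33 to 40% of the year is covered. What is not stated is whether screen failures' events are tabulated. Section 6.2.1 also sends events before dosing to medical history, whereas Section 9.4.3 and Appendix 1 treat those of parent-study vaccinees as adverse events.
- *Seronegative single-dose recipients who decline the injection are barred.* Exclusion 2 names unwilling placebo recipients only. The text is silent on single-dose recipients who decline.
- *The gap hides enhanced respiratory disease.* Table 2 does link that risk to "failure to generate a strong neutralising antibody response". But the outcome is COVID-19, a CESI, and CESI reporting is retained for a year. Seronegativity at about four to five months may also reflect waning rather than failure to respond.
- *The Cohort 1b between-study event rate is forced to near zero.* This is true only of diagnoses meeting exclusion 4. Minor MAAEs and other events can still appear, and some out-of-range laboratory values may be approved or retested.

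Section 9.4.1 also has SAEs followed to resolution, and Section 9.4.4.6 has the Sponsor follow up SAEs and CESIs in anyone vaccinated within 12 months. Both pursue events already reported. Neither schedules contact that would detect new ones.

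**Conclusion.** The point holds as a gap in routing with an informative consequence. Read together, the synopsis, Sections 3.2, 3.8.1 and 5.2, and SAP Section 3.2 leave a seronegative single-dose vaccinee who fails the dosing-only criteria without scheduled SAE, MAAE or NOCD follow-up after Screening. About 60 to 67% of the 12 months after vaccination is lost for each such subject, CESI reporting excepted. This rests on the SAP's nominal 147 days and on sites applying the entry criteria as written.

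The gap also catches people who fail for travel, medication use, laboratory values or another SARS-CoV-2 vaccine. The selection on illness comes chiefly through exclusion 4. The number affected is unknown, and the analysis is descriptive, so no test result is at risk. In a study of approximately 99 and at most 166 subjects, however, one serious new diagnosis missing from the tables could change how the safety record reads.

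**What to change.** Reconcile the synopsis, Sections 3.2, 3.8.1, 5.2 and 10.2, and SAP Sections 3.2 and 5.2, as follows:

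- Any parent-study ARCT-021 recipient who meets inclusions 1 to 3 and does not meet exclusion 1, but is not dosed here, may enter the existing schedule for subjects not receiving ARCT-021. State explicitly whether this covers single-dose recipients who decline the injection.
- Record their between-study SAEs, MAAEs, NOCDs and CESIs as for other parent-study vaccinees.
- Show them as a separate Cohort 2 row: seronegative, not re-dosed.

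No dosing criterion changes.

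The SAP is for an interim analysis with Day 57 data from Cohort 1, so screening may already be complete. In that case:

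- Report screen failures among parent-study vaccinees by serostatus and reason, with the events solicited at Screening.
- Add a footnote to the Cohort 1b pre-study display saying that it excludes subjects who failed the dosing criteria.

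The cost is amendment wording, one more table row and a few subjects attending five existing visits. Cohort 2 becomes slightly more heterogeneous, which the separate row keeps visible. The reporting-only route costs one table and a footnote, but cannot recover the follow-up.
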